3.5 Analysis Populations

China participants randomized after enrollment of the global portion is closed (if any) will not be included in the global analysis populations. The China subpopulation (including China participants in global portion and China extension portion) will also be analyzed separately per local regulatory requirements.

3.5.1 Efficacy Analysis Populations

The ITT population will serve as the primary population for the analysis of efficacy data in this study. The ITT population consists of all randomized participants. Participants will be analyzed in the treatment arm to which they are randomized. Details of the approach to handling missing data are provided in Section 3.6.1.4.

3.5.2 Safety Analysis Populations

Safety Analyses will be conducted in the APaT population, which consists of all randomized participants who received at least one dose of study treatment. Participants will be included in the treatment group corresponding to the study treatment they actually received for the analysis of safety data using the APaT population. This will be the treatment group to which they are randomized except for participants who take incorrect study treatment for the entire treatment period; such participants will be included in the treatment group corresponding to the study treatment actually received.

At least one laboratory or vital sign measurement obtained subsequent to at least one dose of study treatment is required for inclusion in the analysis of the respective safety parameter. To assess change from baseline, a baseline measurement is also required.

3.5.3 PRO Analysis Populations

The PRO analyses are based on the PRO FAS population, defined as all randomized participants who have at least one PRO assessment available for the specific endpoint and have received at least one dose of the study intervention. Participants will be analyzed in the treatment group to which they are randomized.

3.6 Statistical Methods

Statistical testing and inference for safety analyses are described in Section 3.6.2. Efficacy results that will be deemed to be statistically significant after consideration of the Type I error control strategy are described in Section 3.8, Multiplicity. Nominal p-values may be computed for other efficacy analyses, but should be interpreted with caution due to potential issues of multiplicity, sample size, etc.

3.6.1 Statistical Methods for Efficacy Analyses

This section describes the statistical methods that address the primary and secondary objectives.

The stratification factors used for randomization (see Section 6.3.2 of protocol) will be applied to all stratified analyses, in particular, the stratified log-rank test, stratified Cox model, and stratified M&N method [1].

3.6.1.1 Overall Survival

The nonparametric Kaplan-Meier method will be used to estimate the survival curves. The treatment difference in survival will be assessed by the stratified log-rank test. A stratified Cox proportional hazard model with Efron's method of tie handling will be used to assess the magnitude of the treatment difference (ie, the HR). The HR and its 95% CI from the stratified Cox model with a single treatment covariate will be reported. The stratification factors used for randomization (see Section 6.3.2 of protocol) will be applied to both the stratified log-rank test and the stratified Cox model. Participants without documented death at the time of analysis will be censored at the date the participant was last known to be alive.

3.6.1.2 Progression-Free Survival

The nonparametric Kaplan-Meier method will be used to estimate the PFS curve in each treatment group. The treatment difference in PFS will be assessed by the stratified log-rank test. A stratified Cox proportional hazard model with Efron's method of tie handling will be used to assess the magnitude of the treatment difference (ie, HR) between the treatment arms. The HR and its 95% CI from the stratified Cox model with a single treatment covariate will be reported. The stratification factors used for randomization (see Section 6.3.2 of protocol) will be applied to both the stratified log-rank test and the stratified Cox model.

Since disease progression is assessed periodically, PD can occur any time in the time interval between the last assessment where PD was not documented and the assessment when PD is documented. The true date of disease progression will be approximated by the earlier of the date of the first assessment at which PD is objectively documented per RECIST 1.1 by BICR and the date of death. Death is always considered a PD event. Surgical participants (i.e., those who undergo oncologic surgeries with curative intent) will be followed to the disease recurrence after the surgery for PFS analysis.

For the primary analysis, any participant who experiences an event (PD or death) immediately after 2 or more missed disease assessments will be censored at the last disease assessment prior to the missed visits. In addition, any participant who initiates new anti-cancer therapy prior to documented progression will be censored at the last disease assessment prior to the initiation of new anti-cancer therapy. Participants who do not start new anti-cancer therapy and who do not experience an event will be censored at the last disease assessment. If a participant meets multiple criteria for censoring, the censoring criterion that occurs earliest will be applied.

In order to evaluate the robustness of the PFS endpoint per RECIST 1.1 by BICR, 2 sensitivity analyses with different sets of censoring rules will be performed. The first sensitivity analysis follows the intention-to-treat principle. That is, PDs/deaths are counted as events regardless of missed study visits or initiation of new anti-cancer therapy. The second sensitivity analysis considers initiation of new anticancer treatment or discontinuation of treatment due to reasons other than complete response, whichever occurs later, to be a PD event for participants without documented PD or death. If a participant meets multiple criteria for censoring, the censoring criterion that occurs earliest will be applied. The censoring rules for the primary and sensitivity analyses are summarized in [Table 1](#).

Table 1 Censoring Rules for Primary and Sensitivity Analyses of PFS

Situation	Primary Analysis	Sensitivity Analysis 1	Sensitivity Analysis 2
PD or death documented after ≤ 1 missed disease assessment, and before new anti-cancer therapy, if any	Progressed at date of documented PD or death	Progressed at date of documented PD or death	Progressed at date of documented PD or death
PD or death documented immediately after ≥ 2 consecutive missed disease assessments, or after new anti-cancer therapy	Censored at last disease assessment prior to the earlier date of ≥ 2 consecutive missed disease assessment and new anti-cancer therapy, if any	Progressed at date of documented PD or death	Progressed at date of documented PD or death
No PD and no death; and new anticancer treatment is not initiated	Censored at last disease assessment	Censored at last disease assessment	Progressed at treatment discontinuation due to reasons other than complete response; otherwise censored at last disease assessment if still on study treatment or completed study treatment.
No PD and no death; new anticancer treatment is initiated	Censored at last disease assessment before new anticancer treatment	Censored at last disease assessment	Progressed at date of new anticancer treatment
Abbreviations: PD = progressive disease			

3.6.1.3 Objective Response Rate

The stratified M&N method will be used for the comparison of ORR between 2 treatment groups. The difference in ORR and its 95% CI from the stratified M&N method with strata weighting by sample size will be reported. The stratification factors used for randomization (see Section 6.3.2 of protocol) will be applied to the analysis.

The point estimate of ORR will be provided by treatment group, together with 95% CI using exact binomial method proposed by Clopper and Pearson (1934) [6].

3.6.1.4 Duration of Response

If sample size permits, DOR will be summarized descriptively using Kaplan-Meier method. Only the subset of participants who show a confirmed complete response or partial response will be included in this analysis. Censoring rules for DOR are summarized in [Table 2](#).

For each DOR analysis, a corresponding summary of the reasons responding participants are censored will also be provided. Responding participants who are alive, have not progressed, have not initiated new anti-cancer treatment, have not been determined to be lost to follow-up, and have had a disease assessment within ~5 months of the data cutoff date are considered ongoing responders at the time of analysis. If a participant meets multiple criteria for censoring, the censoring criterion that occurs earliest will be applied. For surgical participants, DOR will be defined using time from first documented evidence of response to the disease recurrence or death after the surgery.

Table 2 Censoring Rules for DOR

Situation	Date of Progression or Censoring	Outcome
No progression nor death, no new anti-cancer therapy initiated	Last adequate disease assessment	Censor (non-event)
No progression nor death, new anti-cancer therapy initiated	Last adequate disease assessment before new anti-cancer therapy initiated	Censor (non-event)
Death or progression immediately after ≥ 2 consecutive missed disease assessments or after new anti-cancer therapy, if any	Earlier date of last adequate disease assessment prior to ≥ 2 missed adequate disease assessments and new anti-cancer therapy, if any	Censor (non-event)
Death or progression after ≤ 1 missed disease assessments and before new anti-cancer therapy, if any	PD or death	End of response (Event)
A missed disease assessment includes any assessment that is not obtained or is considered inadequate for evaluation of response.		

3.6.1.5 Analysis Strategy for Key Efficacy Variables

A summary of the primary analysis strategy for the key efficacy endpoints is provided in [Table 3](#).

Table 3 Analysis Strategy for Key Efficacy Variables

Endpoint/Variable	Statistical Method	Analysis Population	Missing Data Approach
Primary Analyses			
OS	Testing: stratified log-rank test Estimation: Stratified Cox model with Efron's tie handling method	ITT	Censored at the date participant last known to be alive
Key Secondary Analyses			
PFS per RECIST 1.1 by BICR	Testing: stratified log-rank test Estimation: Stratified Cox model with Efron's tie handling method	ITT	Censored according to rules in Table 1
ORR per RECIST 1.1 by BICR	Testing and estimation: stratified Miettinen and Nurminen method	ITT	Participants with missing data are considered non-responders
Abbreviations: BICR = blinded independent central review; ITT = intent-to-treat; ORR = objective response rate; OS = overall survival; PFS = progression-free survival; RECIST 1.1 = Response Evaluation Criteria in Solid Tumors.			

3.6.2 Statistical Methods for Safety Analyses

Safety and tolerability will be assessed by clinical review of all relevant parameters including AEs, laboratory tests and vital signs.

The analysis of safety results will follow a tiered approach ([Table 4](#)). The tiers differ with respect to the analyses that will be performed. Adverse events (specific terms as well as system organ class terms) and events that meet predefined limits of change in laboratory and vital signs are either prespecified as “Tier 1” endpoints or will be classified as belonging to “Tier 2” or “Tier 3” based on the number of events observed.

Tier 1 Events

Safety parameters or AEs of special interest that are identified a priori constitute “Tier 1” safety endpoints that will be subject to inferential testing for statistical significance. There are no Tier 1 events for this protocol. Adverse events that are immune-mediated or potentially immune-

mediated are well documented and will be evaluated separately; however, these events have been characterized consistently throughout the pembrolizumab clinical development program, and determination of statistical significance is not expected to add value to the safety evaluation. The combination of lenvatinib plus pembrolizumab has not been found to be associated with any new safety signals. Finally, there are no known AEs associated with participants with CRC for which determination of a p-value is expected to impact the safety assessment.

Tier 2 Events

Tier 2 parameters will be assessed via point estimates with 95% CIs provided for differences in the proportion of participants with events using the M&N method, an unconditional, asymptotic method [1].

Membership in Tier 2 requires that at least 10% of participants in any treatment group exhibit the event; all other AEs and predefined limits of change will belong to Tier 3. The threshold of at least 10% of participants was chosen for Tier 2 events because the population enrolled in this study is in critical condition and usually experiences various AEs of similar types regardless of treatment; events reported less frequently than 10% of participants would obscure the assessment of the overall safety profile and add little to the interpretation of potentially meaningful treatment differences. In addition, Grade 3 to 5 AEs ($\geq 5\%$ of participants in 1 of the treatment groups) and SAEs ($\geq 5\%$ of participants in 1 of the treatment groups) will be considered Tier 2 endpoints. Because many 95% CIs may be provided without adjustment for multiplicity, the CIs should be regarded as a helpful descriptive measure to be used in safety review, not as a formal method for assessing the statistical significance of the between-group differences.

Tier 3 Events

Safety endpoints that are not Tier 1 or 2 events are considered Tier 3 events. The broad AE categories consisting of the proportion of participants with any AE, a drug related AE, a serious AE, an AE which is both drug-related and serious, a Grade 3-5 AE, a drug-related Grade 3-5 AE, and discontinuation due to an AE will be considered Tier 3 endpoints. Only point estimates by treatment group are provided for Tier 3 safety parameters.

Continuous Safety Measures

For continuous measures such as changes from baseline in laboratory and vital signs parameters, summary statistics for baseline, on-treatment, and change from baseline values will be provided by treatment group in table format.

Table 4 Analysis Strategy for Safety Parameters

Safety Tier	Safety Endpoint	95% CI for Treatment Comparison	Descriptive Statistics
Tier 2	Grade 3-5 AE (incidence $\geq 5\%$ of participants in one of the treatment groups)	X	X
	Serious AE (incidence $\geq 5\%$ of participants in one of the treatment groups)	X	X
	AEs (incidence $\geq 10\%$ of participants in one of the treatment groups)	X	X
Tier 3	Any AE		X
	Any Grade 3-5 AE		X
	Any Serious AE		X
	Any Drug-Related AE		X
	Any Serious and Drug-Related AE		X
	Any Grade 3-5 and Drug-Related AE		X
	Discontinuation due to AE		X
	Death		X
	Specific AEs, SOCs (incidence $< 10\%$ of participants in all of the treatment groups)		X
	Change from Baseline Results (lab toxicity shift, vital signs)		X
Abbreviations: AE = adverse events; SOC = standard of care			

To properly account for the potential difference in follow-up time between the study arms, AE incidence adjusted for treatment exposure analyses may be performed as appropriate.

Time to Grade 3-5 AE

Additional exploratory analysis may be performed on the time to the first Grade 3-5 AE. The time to the first Grade 3-5 AE is defined as the time from the first day of study drug to the first event of a Grade 3-5 AE. Summary statistics will be provided.

3.6.3 Statistical Methods for Patient-Reported Outcome Analyses

This section describes the planned analyses for the PRO endpoints.

3.6.3.1 PRO Scoring Algorithm

EORTC QLQ-C30 Scoring: Each scale or item is scored between 0 and 100, according to the EORTC QLQ-C30 standard scoring algorithm [7]. For global health status/quality of life and all functional scales, a higher value indicates a better level of function; for symptom scales and items, a higher value indicates increased severity of symptoms.

EORTC QLQ-CR29 Scoring: All of the scales and single-item measures range in score from 0 to 100. A high score for the functional scale and functional single-items represents a high level of functioning, whereas a high score for the symptom scales and symptom single-items represents a high level of symptomatology or problems.

3.6.3.2 PRO Completion and Compliance Summary

Completion and compliance of EORTC QLQ-C30, EORTC QLQ-CR29, and EQ-5D by visit and by treatment will be described. Numbers and percentages of complete and missing data at each visit will be summarized.

Completion rate of treated participants (CR-T) at a specific visit for a given instrument is defined as the number of treated participants who complete at least one item on that PRO instrument over the number of treated participants in the PRO analysis population.

$$\text{CR-T} = \frac{\text{Number of treated participants who complete at least one item}}{\text{Number of treated participants in the PRO analysis population}}$$

The completion rate is expected to decrease at later visits during study period for reasons such as study design (e.g., PROs not required following progression), patient discontinuation, etc. Therefore, the compliance rate (CR-E) will also be presented in addition to completion rate. CR E is defined as the number of treated participants who complete at least one item of the instrument over number of participants who are expected to complete the PRO assessment at that visit, excluding participants missing by design such as death, discontinuation, translation not available.

$$\text{CR-E} = \frac{\text{Number of treated participants who complete at least one item}}{\text{Number of treated participants who are expected to complete}}$$

The completion and compliance status will be summarized as below:

- Completed as scheduled
- Not completed as scheduled
- Off-study: not scheduled to be completed.

The reasons for non-completion as scheduled of these measures are collected using “miss_mode” forms filled by site personnel and will be summarized in a table format. The schedule (study visits and estimated study times) and mapping of study visit to analysis visit for PRO data collection is provided in [Table 5](#).

Table 5 PRO Data Collection Schedule and Mapping of Study Visit to Analysis Visit

Treatment Week	Week 0	Week 2	Week 4	Week 6	Week 8	Week 10	Week 12	Week 16	Week 20	Week 24	Week 28
Day	1	15	29	43	57	71	85	113	141	169	197
Range (relative day to first dose date)	[-5, 8]	[9, 22]	[23, 36]	[37, 50]	[51, 64]	[65, 78]	[79, 99]	[100, 127]	[128, 155]	[156, 183]	[184, 211]
Treatment Week	Week 32	Week 36	Week 40	Week 44	Week 52	Week 60	Week 68	Week 76	Week 84	Week 92	Week 100
Day	225	253	281	309	365	421	477	533	589	645	701
Range (relative day to first dose date)	[212, 239]	[240, 267]	[268, 295]	[296, 337]	[338, 393]	[394, 449]	[450, 505]	[506, 561]	[562, 617]	[618, 673]	[674, 729]

3.6.3.3 Change from Baseline

The time point for the mean change from baseline analysis is defined as the latest time point at which CR-T $\geq 60\%$ and CR-E $\geq 80\%$, and week 8 was selected based on blinded data review prior to the database lock for any PRO analysis.

To assess the treatment effects on the PRO score change from baseline in the EORTC QLQ-C30 global health status/QoL, physical functioning and appetite loss, EORTC QLQ-CR29 bloating scores, and EQ-5D-5L VAS, a constrained longitudinal data analysis (cLDA) model proposed by Liang and Zeger [8] will be applied, with the PRO score as the response variable, and treatment, time, the treatment by time interaction, and the stratification factors used for randomization (see Section 6.3.2 of protocol) as covariates. The treatment difference in terms of least square mean change from baseline will be estimated from this model together with 95% CI. Model-based least square mean with 95% CI will be provided by treatment group for PRO scores at baseline and post-baseline time point.

The technical details on the cLDA model are in the appendix of this sSAP.

Line plots for the empirical mean change from baseline in EORTC QLQ-C30 global health status/QoL, physical functioning and appetite loss, EORTC QLQ-CR29 bloating scores, and EQ-5D-5L VAS score will be provided across all time points as a supportive analysis.

In addition, the model-based LS mean change from baseline to the specified post-baseline time point together with 95% CI will be plotted in bar charts for EORTC QLQ-C30 global health status/QoL scores, all functioning and symptom scores, and for EORTC QLQ-CR29 all functioning and symptom scores.

3.6.3.4 Time-to-First-Deterioration

The Kaplan-Meier method will be used to estimate the TTD curve for each treatment group. The estimate of median time to deterioration and its 95% confidence interval will be obtained from the Kaplan-Meier estimates. The treatment difference in TTD will be assessed by the stratified log-rank test. A stratified Cox proportional hazard model with Efron's method of tie handling and with a single treatment covariate will be used to assess the magnitude of the

treatment difference (ie, HR). The HR and its 95% CI will be reported. The stratification factors used for randomization (see Section 6.3.2 of protocol) will be used as the stratification factors in both the stratified log-rank test and the stratified Cox model.

The approach for the TTD analysis will be based on the assumption of non-informative censoring. The participants who do not have deterioration on the last date of evaluation will be censored. [Table 6](#) provides censoring rule for TTD analysis.

Table 6 Censoring Rules for Time to First Deterioration

Scenario	Outcome
Deterioration documented	Event observed at time of assessment (first deterioration)
Ongoing or discontinued from study without deterioration	Right censored at time of last assessment
No baseline assessments	Right censored at treatment start date

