3 ANALYTICAL AND METHODOLOGICAL DETAILS

3.1 Statistical Analysis Plan Summary

Key elements of the statistical analysis plan are summarized below; the comprehensive plan is provided in Sections 3.2-3.12.

Study Design Overview	A Phase 3 randomized study of lenvatinib in combination with pembrolizumab versus standard of care in participants with metastatic colorectal cancer who have received and progressed on or after or became intolerant to prior treatment
Treatment Assignment	Approximately 434 participants will be randomized in a 1:1 ratio between two treatment groups: (1) the lenvatinib plus pembrolizumab arm and (2) the SOC arm. Stratification factor is: Presence of liver metastasis (Yes/No). This is an open-label study.
Analysis Populations	Efficacy: ITT Safety: APaT Patient-reported outcome: FAS
Primary Endpoint(s)	Overall survival
Key Secondary Endpoints	Progression-free survival per RECIST 1.1 as assessed by BICR. Objective response rate per RECIST 1.1 as assessed by BICR.

Statistical Methods for Key Efficacy Analyses	The primary hypothesis testing for OS and secondary hypothesis testing for PFS will be evaluated by comparing the experimental group to the control group using a stratified log-rank test. The HR will be estimated using a stratified Cox regression model. Event rates over time will be estimated within each treatment group using the Kaplan-Meier method. The stratified M&N method with strata weighted by sample size will be used for analysis of ORR [1].
Statistical Methods for Key Safety Analyses	For analyses in which 95% CIs will be provided for between-treatment differences in the percentage of participants with events, these analyses will be performed using the M&N method.

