3.4.3 PRO Endpoints

- Change from baseline in EORTC QLQ-C30 global health status/QoL, physical functioning and appetite loss and EORTC QLQ-CR29 bloating scores for the combination of lenvatinib plus pembrolizumab versus SOC
- Time to first deterioration (TTD) in EORTC QLQ-C30 global health status/QoL, physical functioning and appetite loss and EORTC QLQ-CR29 bloating scores for the combination of lenvatinib plus pembrolizumab versus SOC

Based on prior literature (Bjordal, et al., 2000; Osoba D, 1998 [3]; King, 1996 [4]), a 10 points or greater worsening from baseline for each scale represents a clinically relevant deterioration for EORTC. TTD is defined as the time from baseline to the first onset of a 10 or more points deterioration from baseline.

- Change from baseline in **CCI** [REDACTED] for the combination of lenvatinib plus pembrolizumab versus SOC
- **CCI** [REDACTED]

The assessment for possible PRO response at a time point considering subsequent confirmation is defined as follows:

Assessment Category at a time point (one analysis visit)	Change from baseline at a time point (one analysis visit)	Change from baseline at the subsequent time point (the next consecutive analysis visit)
Improvement	score improved from baseline by ≥ 10 points	score improved from baseline by ≥ 10 points
Stability	score improved from baseline by ≥ 10 points	score improved or worsened from baseline by < 10 points
	score improved or worsened from baseline by < 10 points	score improved or worsened from baseline by < 10 points
	score improved or worsened from baseline by < 10 points	score improved from baseline by ≥ 10 points
Worsening	score worsened from baseline by ≥ 10 points	not required
Unconfirmed	A time point assessment that doesn't meet any of the above criteria.	

The overall improvement is defined as the best observed PRO response that is an improvement among all post-baseline assessments by timepoint. The overall improvement + stability is defined as the best observed PRO response that is an improvement or stability among all post-baseline assessments by timepoint.

Changes from baseline in EORTC QLQ-C30 scores will also be interpreted according to recent subscale-specific guidelines, which indicate that clinically meaningful differences vary by scale (Cocks et al., 2012) [5].

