3.6.3.5 Overall Improvement / Overall Improvement and Stability

Overall improvement rate will be analyzed, which is defined as the proportion of participants who have achieved an overall improvement as defined in Section 3.4.3 PRO Endpoints. Stratified Miettinen and Nurminen's method will be used for comparison of the overall improvement rate between the treatment groups. The difference in overall improvement rate and its 95% CI from the stratified Miettinen and Nurminen's method with strata weighting by sample size will be provided. The stratification factors used for randomization (See Section 6.3.2 of protocol) will be applied to the analysis.

The point estimate of overall improvement rate will be provided by treatment group, together with 95% CI using exact binomial method by Clopper and Pearson (1934) [\[6\]](#).

The same method will be used to analyze overall improvement and stability rate, which is defined as the proportion of participants who have achieved overall improvement and stability as defined in Section 3.4.3 PRO Endpoints.

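### The comparisons of time to deterioration and overall improvement leave out the baseline PRO score against which both endpoints are defined; they stay valid but give up efficiency and carry chance baseline imbalance

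*SAP*

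**What the plan says.** Section 3.4.3 defines deterioration against the participant's own starting value: "TTD is defined as the time from baseline to the first onset of a 10 or more points deterioration from baseline". Improvement at a visit requires "score improved from baseline by ≥ 10 points", repeated at the next analysis visit. Section 3.6.3.1 bounds the QLQ-C30 scores: "Each scale or item is scored between 0 and 100"; the QLQ-CR29 scores have the same range.

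For TTD, Section 3.6.3.4 uses a Cox model with Efron's "method of tie handling and with a single treatment covariate will be used to assess the magnitude" of the treatment difference. The randomization factors "will be used as the stratification factors in both the stratified log-rank test and the stratified Cox model". Section 3.1 names only one such factor: "Stratification factor is: Presence of liver metastasis (Yes/No".

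For overall improvement, Section 3.6.3.5 says that the stratified Miettinen and Nurminen "method will be used for comparison of the overall improvement rate between the treatment groups". The difference and 95% CI from that "method with strata weighting by sample size will be provided". Improvement plus stability is handled the same way.

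Sections 3.6.3.3 and 4.2 analyse mean change on the same EORTC scales by cLDA. There the baseline score is part of the response vector, and its mean is constrained to be equal in the two arms.

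**The concern.** An endpoint that counts 10-point moves from a participant's own baseline depends on where that participant starts. Someone within 10 points of the best score cannot improve, and someone within 10 points of the worst cannot deteriorate. Between those ends, regression to the mean makes a good starting score more likely to be followed by a fall and a poor one by a rise. Neither comparison uses this information, although the score exists for everyone who can have an event.

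Two things follow. The comparisons are less efficient than they could be. And if the arms differ by chance at baseline, the difference passes into the TTD hazard ratio and the improvement difference, whereas cLDA accounts for it. Part of any disagreement among PRO results on the same instrument could then come from baseline imbalance rather than treatment, and the SAP gives no reason for treating baseline differently.

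**Working it through.** The SAP gives no PRO standard deviation, correlation, effect size, event count or power, so there is no planned figure to reproduce. Its own input is 434 participants randomized 1:1, about 217 per arm (Section 3.1). The rest is assumed and shown as a range.

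**1. Size of chance imbalance.** The SE of the standardized baseline difference is sqrt(2/n) = sqrt(2/217) = 0.096 SD. The 95% range is ±1.96 × 0.096 = ±0.19 SD, or ±3.8 points at SD 20 and ±4.7 at SD 25. One SE at SD 22 is about 2.1 points.

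**2. Closed form for improvement.** Suppose a share s of participants starts too near the best score to improve and the others improve with probability q, so that p = (1-s)q. Knowing who can improve reduces the outcome variance by 1 - (1-s)q(1-q)/[p(1-p)].
- s = 0.1, q = 0.2: p = 0.18; 1 - 0.144/0.1476 = 2%.
- s = 0.5, q = 0.4: p = 0.20; 1 - 0.12/0.16 = 25%.

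**3. Simulation.** 1,500 trials per setting, 200 per arm, visits at Weeks 2-24 as in Table 5, and PRO follow-up ending at an exponential time with mean 20 weeks in both arms. Two scale types were used: a multi-item scale (SD 22, 15% starting at or near the best score) and a four-level item (SD 22 × 1.2, 42% at the best score). Correlation was 0.5 or 0.7, with a true shift of 0 or 5 points. Liver-metastasis strata were left out. The Cox model used Efron ties with and without baseline; the risk difference was taken with and without a linear-model adjustment for baseline and its square. Results at a 5-point shift, unadjusted → adjusted:

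| Scale, correlation | TTD log HR | Model SE of log HR | TTD power | SE of improvement difference | Variance cut | Improvement power |
|---|---|---|---|---|---|---|
| Multi-item, 0.5 | -0.288 → -0.333 | 0.136 → 0.136 | 55.2% → 68.1% | 0.0432 → 0.0392 | 17.5% | 40.5% → 48.1% |
| Multi-item, 0.7 | -0.390 → -0.418 | 0.145 → 0.146 | 76.1% → 82.1% | 0.0394 → 0.0372 | 10.8% | 55.7% → 61.3% |
| Four-level, 0.5 | -0.239 → -0.273 | 0.139 → 0.139 | 39.9% → 50.2% | 0.0402 → 0.0348 | 25.2% | 20.7% → 27.2% |
| Four-level, 0.7 | -0.308 → -0.327 | 0.150 → 0.150 | 53.6% → 58.9% | 0.0362 → 0.0327 | 18.4% | 26.6% → 30.6% |

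With no shift, the variance cut for improvement was 9.8-23.4%. Unadjusted rejection was 4.0-5.0% for Cox and 4.7-5.4% for the risk difference.

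**4. Imbalance carried into TTD.** The unadjusted log HR moved by 0.45-0.62 per SD of baseline difference. One SE gives exp(0.45 × 0.096) = 1.04 to exp(0.62 × 0.096) = 1.06. At the edge of the 95% range and the steeper slope, exp(±0.62 × 0.19) = 0.89 to 1.12. The correlation between estimate and imbalance was 0.31-0.45 in absolute value before adjustment and -0.04 to 0.02 after.

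**5. Second simulation, other assumptions.** 420 participants, mean 65, SD 22, a 4-point effect, PROs ending at progression with a PFS HR of 0.65, and 6.67-point score steps. TTD power rose from 0.29 to 0.35, 0.37 to 0.42 and 0.50 to 0.55 at correlations 0.5, 0.6 and 0.7. A 2-point imbalance moved the HR by 4-5% and the improvement difference by 1.2-1.7 percentage points. The SD of the improvement difference fell 5-8%, which in variance is 1 - 0.95² = 10% to 1 - 0.92² = 15%. The two simulations agree in direction and roughly in size.

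**The case against.** The case for leaving the plan alone is substantial. Unadjusted stratified log-rank, Cox and M&N analyses are conventional, and OS, PFS and ORR are handled the same way. Null rejection stays near 5%. A 1-SE imbalance moves the TTD log HR by about a third of its standard error (0.049/0.14 for a 5% shift), which is sampling variation that the reported CI already covers. The PRO endpoints lie outside the alpha-controlled family of Section 3.8, and Section 3.6 already advises caution with nominal p-values. TTD and a Week 8 mean change can also differ with perfectly balanced arms. All of this stands and limits the weight of the point.

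A reader might infer that both comparisons lose precision in the ordinary sense. That fails for TTD: the Cox standard error does not fall. The gain is power, because the conditional log HR lies further from zero, and a conditional HR is a different quantity from the planned one. A reader might also infer that baseline largely decides who can move 10 points. The SAP gives no baseline distribution to support that. Baseline decides fully only near the scale ends, and under the assumed inputs it accounts for about 10-25% of the variance in improvement.

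What remains after these concessions is the improvement comparison, where a standardized risk difference targets the same quantity with a smaller variance, and the removal of imbalance shift from both endpoints. Both are gains in estimation, which is the role of these endpoints.

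**Conclusion.** The point holds as an efficiency and consistency weakness. It is not an error, and the documents do not support reading the planned PRO comparisons as biased or invalid. Neither comparison uses the baseline score, although both endpoints are defined against it and cLDA on the same scales does use it.

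The sizes rest on the assumed SDs, correlations, score steps and follow-up, none of which the SAP gives. Parts of Section 3.4.3 and the last row of Table 7 are blacked out, so the scales covered by the improvement analysis and its status cannot be seen; its method in Section 3.6.3.5 is visible. OS, PFS and ORR are not affected.

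**What to change.** 1. **Section 3.6.3.5.** Estimate the improvement and improvement-plus-stability differences with adjustment for the scale's baseline score and liver metastasis, and report a standardized (marginal) risk difference with 95% CI. Allow a nonlinear baseline effect, since the scale ends make a straight line doubtful. Section 3.5.3 requires only one PRO assessment, so the FAS can include participants without a baseline score. State that they stay in the denominator in the same way as in the M&N analysis, so that both results refer to the same people. Report the M&N result alongside.

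2. **Section 3.6.3.4.** Keep the stratified log-rank test and the single-covariate Cox HR. Prespecify a supportive stratified Cox model that adds the baseline score, and label its HR as conditional on baseline. Participants without a baseline are already censored at treatment start (Table 6), so no TTD information is lost.

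The cost is sSAP wording and a little programming with data already collected, plus a supportive TTD HR that is conditional and should not be read as interchangeable with the planned one (0.79 against 0.80 at correlation 0.6 in the second simulation). The change should be written down before treatment-level PRO results are seen, because adding it after an imbalance appears would look selective.
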